A small-scale two-group randomized controlled (RCT) pilot study of 28 African American female caregivers, age 40 and older with hypertension, will be conducted. We will determine the feasibility and acceptability of Mindfulness in Motion (MIM) plus the Dietary Approaches to Stop Hypertension (DASH). Participants will be randomized to either the MIM DASH intervention or the Alzheimer's Association Caregiver Training (attention control) delivered in 8 weekly, 1-hour group sessions via telehealth (video and telephone access). After completion of the intervention, both groups will receive eight weekly and then four monthly coaching calls or surveys through Mosio over the 9 months. To our knowledge, this is the first study that a) systematically employs one of the **Science of Behavioral Change key mechanisms underlying successful adoption** of health behaviors—stress reactivity/stress resilience and b) focuses solely on African American female caregivers of people living with dementia. The study aims are to:

AlM 1. Determine the feasibility and acceptability of MIM DASH and Caregiver Training for African American female caregivers with hypertension. Hypothesis: MIM DASH and Caregiver Training groups will be feasible and acceptable to caregivers. Method: We will track *feasibility*: screening to enrollment, attendance, attrition, completion of data collection procedures; and *acceptability*: treatment-specific preference ratings (prepost intervention). The Credibility Scale will capture attitudes towards the treatment condition and the participants' expectation of benefit once the treatment has been explained. Analysis: Feasibility and acceptability will be examined through descriptive statistics.

AIM 2. Explore the impact of MIM DASH as compared to Caregiving Training on caregiver stress and QOL. Hypothesis: MIM DASH group will have improved caregiver stress and QOL as compared to the Caregiver Training group. Method: The Perceived Stress Scale will be used as a measure of *caregiver stress* and the level of cortisol extracted from hair will be a proxy measure of *chronic stress*. The World Health Organization-5 will be used to measure QOL. The data will be collected in person and documented in REDCap at baseline, 3, and 9 months post-intervention. Analysis: We will conduct intent-to treat analysis and the fixed effect of MIM DASH intervention will be examined by mixed effects models.

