The **data collection** measures will be administered in both groups at baseline, 3, and 9 months. The study team will attempt to collect data within 8 weeks of the anticipated study visit dates. Data collection will take no longer than 120 minutes for each data collection session. Data collection will take place in the setting that is most convenient for the participant. For example, home or at the College of Nursing. Participant demographics and comorbidities will be collected at baseline. All other measures will be collected at baseline to 3, and 9 months as listed in Table 1. To accommodate the participants, who are caregivers, we will have the option for the study visits to be broken up into smaller 1 hour visits. Additionally, data that does not require an in person visit, such as questionnaires/surveys may be completed via phone or Zoom.

At baseline, we will administer the 6-item Newest Vital Sign as to measure health literacy. The Newest Vital Sign has high internal consistency (Cronbach's Alpha = 0.74). Validation against the Test of Functional Health Literacy in Adults demonstrated a Pearson's r of 0.49 and an area under the ROC curve of 0.81 (Table 1). Scores range from 0-6 with lower scores indicating lower health literacy.

For feasibility of recruitment, we will track the number screened per month; number eligible; number enrolled per month; average time delay from screening to enrollment; and the completion of data collection.⁵⁶ For acceptability, we will track treatment-specific preference ratings (pre- and post-intervention). For acceptability, we will track treatment-specific preference ratings (pre- and post-intervention). The participants will complete

IRB Approval date:

Version: 08/08/2023

10/05/2022

the Acceptability of Participant Preferences 13-item Likert-type survey ranging from 1 (strongly disagree) to 5 (strongly agree). Interventionists will keep detailed intervention session records describing participant response to the intervention. For the MIM DASH group, we will collect data regarding usage of self-care equipment (home BP monitor and MyPlate) from follow-up calls or surveys. We will use a credibility scale for both groups regarding the expectation of benefits of the study. The *Credibility Scale* (α = 0.86) measures attitudes towards the treatment condition and the participants' expectation of benefit once the treatment has been explained. ^{59,60}

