	Discrimination in the Healthcare Setting is 7 questions on a Likert scale to measure the stress of discrimination in the healthcare setting as a result of age in ethnicity	X	Х	Х	α= 0.89
	Hair cortisol (chronic stress proxy)	Х		Х	Correlation with 30-day saliva (r = 0.42, p = 0.041) ⁸¹
	WHO-5 (QOL)	Х	Х	Х	Sensitivity (0.93) specificity (0.83)
Depression- PHQ9 Generalized Anxiety DisorderS	PHQ9 has 9 questions to evaluate mild, moderate, or severe depression The Generalized Anxiety Disorder Assessment (GAD-7) is a seven-item instrument that is used to measure or assess the severity of generalized anxiety disorder (GAD).	х	X	X	α =0.90 . α = 0.92
Revised Memory and Behavior Checklist	32-item check-list that assess activities of daily living and problem behaviors in people living with ADRD	X	X	X	α = 0.84
Discrimination	Discrimination in the Healthcare Setting is 7 questions on a Likert scale to measure the stress of discrimination in the healthcare setting as a result of age in ethnicity	Х	X	Х	α = 0.89
Credibility	Credibility Scale		Х		
Acceptability	Acceptability of Participant Preferences Interview questions		Х	Х	

The scale consists of 5 questions rated on a 0 (not at all confident) to 10 (very confident). Higher scores, up to 45, will indicate greater credibility of the treatment condition. This will also aid in determining participants' willingness to be randomized for future studies.

The Perceived Stress Scale has 10-items one a Likert scale with a reference range of 0-30 regarding stress over the past month. Hair cortisol (HC) will be used as a proxy for chronic stress. To collect the hair samples, approximately 25-75 mg of hair (approximate width of shoelace tip when bunched) will be cut from the posterior vertex region of the scalp as close to the scalp as possible. The posterior vertex has the lowest variation in cortisol levels, and is the preferred area for sampling. Participants will be surveyed on

IRB Approval date:

Version: 08/08/2023

10/05/2022

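### The Credibility Scale is defined as expectation of benefit after the treatment is explained, but Table 1 schedules it only at 3 months, so the plan yields no pre-treatment expectancy score; its stated maximum of 45 is also wrong

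*Combined protocol and SAP*

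**What the plan says.** - **Purpose.** The Aim 1 method in the Introduction says: "The Credibility Scale will capture attitudes towards the treatment condition", together with the women's "expectation of benefit once the treatment has been explained". Measurement/Instrumentation repeats that the scale "measures attitudes towards the treatment condition and the participants' expectation of benefit once the treatment has been explained".
- **Arms.** The same section says: "We will use a credibility scale for both groups regarding the expectation of benefits of the study".
- **Schedule.** In Table 1, the "Credibility Scale" row is blank at baseline, marked at 3M and blank at 9M. The section opens with a general statement that measures are taken in both arms at all three time points, but then defers to the table: "All other measures will be collected at baseline to 3, and 9 months as listed in Table 1".
- **Scoring.** The text after Table 1 reads: "The scale consists of 5 questions rated on a 0 (not at all confident) to 10 (very confident). Higher scores, up to 45". It adds that the scale helps to judge whether women would accept randomisation in later studies.
- **Analysis.** The Aim 1 paragraph of Data Analysis lists six descriptive quantities. None is a credibility score, and no feasibility or acceptability threshold depends on one.

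**The concern.** Expectation of benefit is a property of the participant after she learns what her programme is and before she has been through it. A single rating after the sessions cannot be separated from how she felt the programme went. It falls at the same nominal time point as the Perceived Stress Scale and WHO-5, both self-reported by women who know which programme they attend. If credibility differed between arms at 3M, nobody could say whether the difference preceded the stress and quality-of-life results or followed from them.

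Women who leave data collection before 3M contribute no rating, and some may leave because their programme did not convince them. Enrolling replacements, as the Retention text allows, does not recover those ratings.

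The plan has no substitute. Preference ratings are promised before and after the intervention, but the Acceptability row of Table 1 is marked only at 3M and 9M. Table 1 therefore schedules no rating of the treatment before exposure. Once sessions are under way, a participant's pre-treatment expectation cannot be reconstructed.

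**Working it through.** **1. Is the 3M reading of Table 1 reliable?** The table was extracted from PDF, so the column order needs a check. The hair cortisol and Block food frequency rows both show marks at baseline and 9M with a gap at 3M, and the text confirms that schedule for each. The columns are in order, and the single Credibility mark is at 3M.

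**2. Where does 3M fall relative to treatment?** Inputs: eight weekly sessions (Introduction), a visit window of 8 weeks (Measurement/Instrumentation), and 3 months = 13.0 weeks.

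| Time origin | Nominal 3M visit | Earliest date (minus 8 weeks) |
|---|---|---|
| Start of sessions | week 13.0 | week 5.0 |
| End of sessions (Aims 2 and 3 say post-intervention) | 8 + 13.0 = week 21.0 | week 13.0 |

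Sessions end at week 8, so the nominal visit follows the last session on either reading. With the window, some ratings could come as early as week 5, during the sessions. The Internal Validity section names 1 month (about week 4.3) instead of 3 months. The Retention text mentions a possible wait before sessions, of unstated length. These points make the timing less consistent, but none places the scale between explanation and session 1.

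**3. Who is rated?** The Sampling Plan gives a total of 28, including 28.6% for attrition. The number of completers is not stated, but 28 × (1 − 0.286) = 19.99, or 20, and in reverse 20 / (1 − 0.286) = 28.01. The plan's 28 is thus reproduced with 28.6% read as the share expected to be lost (8/28 = 28.57%).

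- At 28.6% loss: 20 of 28 rated.
- At 50% loss (the earlier MIM DASH trial, Figure 1): 28 × 0.5 = 14 of 28 rated.

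Both assume that all loss precedes 3M. They are lower bounds for that visit, because 28.6% is the allowance for the whole study.

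**4. What precision would an early rating have?** The half-width of the 95% CI for the difference between arms, in SD units, is t(0.975, 2n − 2) × √(2/n), with n per arm. A 1:1 split is assumed; the ratio is not stated.

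| Women rated | n per arm | Half-width (SD) |
|---|---|---|
| 28 | 14 | 2.056 × 0.378 = 0.78 |
| 20 | 10 | 2.101 × 0.447 = 0.94 |
| 14 | 7 | 2.179 × 0.535 = 1.16 |

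An early rating of everyone randomised is more precise, but ±0.78 SD is far too wide to demonstrate equality.

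**5. Scale range.** 5 items × 10 = 50. The stated maximum is 45, which is 5 points (10%) lower.

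**The case against.** The best defence has four parts.

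- **The table may simply have lost a mark.** The general sentence puts measures at all three time points, and the neighbouring Acceptability row also lacks a baseline mark that the text implies. This is plausible. But the text defers to Table 1, and staff following the table would not give the form early. If an early administration was intended, text and table conflict and still need amending.
- **The explanation of treatment sets an earliest point, not a deadline.** A 3M score still describes credibility after exposure. This stands: the scale is not useless at 3M. What it cannot give is expectancy before treatment.
- **The measure is descriptive and nothing hinges on it.** This also stands, and it limits the importance of the point. It does not make the schedule match the stated construct.
- **Leaving sessions is not leaving data collection.** Correct. Only women lost to data collection before 3M go unrated, and the documents do not say how many that will be.

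A reader might go further and infer that the scale is the plan's check that both arms began with equal expectation, and that the check fails. The documents do not support this. The equal-attention design makes such a check natural, but the plan never assigns the scale that role, and Data Analysis specifies no comparison of credibility between arms. With 28 women, no timing of the form could show equality.

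A reader might also want to say by how many points drop-out inflates the mean score. That needs the gap between leavers and stayers. The documents give no such figure, and it could be zero where women leave through illness.

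**Conclusion.** The point holds as a mismatch between construct and schedule. Followed as written, the plan produces no pre-treatment expectancy score in either arm, only a 3M rating that mixes expectation with experience. It comes from as few as 20 of 28 women at the planned attrition, or 14 at the earlier trial's rate, if all loss comes before that visit. The conclusion rests on Table 1 governing the schedule, as the text says it does, and on the nominal visit date; the 8-week window could bring some ratings into the session period.

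The consequence is confined to what Aim 1 can report about expectancy. No threshold or planned test is affected. The scoring discrepancy (50 against 45) is certain, but it is a separate error and adds nothing to the timing argument.

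**What to change.** 1. In Table 1, add a Credibility administration in both arms, after the assigned programme has been explained and before session 1. The end of session 1 is the latest acceptable time, and second best: by then an hour of the programme has been delivered, and women who miss it are not covered. Use a REDCap or Mosio link, or the telephone.
2. In the Aim 1 analysis, name this early rating as the expectancy score. Report it descriptively by arm with 95% confidence intervals, and do not present it as evidence of equality.
3. Keep the 3M rating as a secondary score, labelled as credibility after exposure.
4. Reconcile the general sentence on three time points with the Credibility row of Table 1, and state whether 3M is counted from the start or the end of the sessions.
5. Correct the scoring text: change the maximum of 45, the item count or the item anchors, after checking the instrument. A change of item count alone cannot give 45 while each item still reaches 10 (45 / 10 = 4.5); five items with a top score of 9 would (5 × 9 = 45).

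The cost is one extra five-item form per participant and a minor amendment to Table 1 and the scale text. No extra visit is needed.

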populations. Three key studies: Resources for Enhancing Alzheimer's Caregiver Health (REACH II), Savvy Caregiver, and Enhanced Physical Activity Intervention had a sufficient samples size of African Americans. However, in these studies, African Americans were less likely to experience

success as other populations. The uptake of the intervention was lower among African Americans than other races and no there were no changes noted in self-care or quality of life. None of these studies included mindfulness as a part of the intervention. One study currently underway of African American caregivers by Gaylord et al., is using telephone-delivered mindfulness-based stress reduction. Our intervention, Mindfulness in Motion plus the Dietary Approaches to Stop Hypertension (MIM DASH) compare to the one in Gaylord et al and thus may provide stronger benefit.

There is a strong need for culturally sensitive strategies. Solid empirical evidence demonstrating the effectiveness of the DASH diet in reducing blood pressure. However, African Americans are less likely than Whites to be adherent to the DASH diet. We hypothesize that there are other confounders impacting adherence, specifically chronic caregiver stress.

Stress reactivity/stress resilience is hypothesized as one of the key mechanisms underlying successful change in behaviors. *Stress reactivity* is the physiological response of the body to stress—activation of the cardiovascular system by increasing heart rate and BP. *Stress resilience* is the process of adapting well in the face of significant sources of stress such as caregiver stress. Both are key mechanisms underlying successful change in behaviors. Thus, our multi-model intervention that includes targeting stress resilience/stress reactivity has strong potential.

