For participants randomized to the MIM DASH group, they will be asked to attend an interview with a study staff member that will last approximately 30 minutes. We will ask the participant several questions using an interview format. The answers provided will be used to help us better understand the participant's perception regarding the DASH eating plan and how it could be adapted to better help African Americans reduce hypertension and cardiovascular disease risk. The staff will also record and transcribe the interview that occurs during the course of the study. The interview that occurs will be audio or video recorded and transcribed verbatim. The transcribed interview data will also be saved in REDCap and the recordings from the interview will then be destroyed. The identified information of participants who take part in the interview will be confidential. Qualitative descriptive methods will be employed for content analysis to elucidate emerging themes within the data.

Table 1. Data collection table of variables, measures, months, and reliability/validity statistics for instruments.

Variables	Measures	Psychometrics			
		Baseline	3M	9M	
Pre-Enrollment	AD8	Х			
	NIA COMMON DATA SCREENING				
Post-Enrollment	NIA COMMON DATA ENROLLMENT	Х			
Biologic	Age in years	Х			
	List of comorbidities	Х			
Newest Vital Sign	Measure health literacy (VS Score Sheet)	Х			α = 0.74
Self-care behaviors	Stress skills management practices	Х	Х	Х	$\alpha = 0.71^{75}$
	Block food frequency questionnaire (FFQ Booklet)	Х		Х	Test-retest
	DASH index-calculated from the block food frequency questionnaire	X		Х	reliability, r=0.59 ⁷⁶
					Mean correlation coefficient
					between
					frequencies of intake of 55
					foods assessed
					by 2 FFQ 12 months apart =
					0.57. ⁷⁷
	Medication list and BP log	Х	Х	Х	
	Krousel-Wood Medication Adherence	Х	X	X	C statistic= 0.704 ⁷⁸
Stress reactivity	Daily inventory of stressful events	Х	Х	Х	(Kappa) ranged
/stress resilience					from 0.66 to 0.95 ⁷⁹

IRB Approval date:

Version: 08/08/2023

10/05/2022

ariables Measures		Psychometrics			
	Pittsburgh stress battery	X	X	X	Heart rate α =0.93; systolic BP; and α =0.92 diastolic BP α =0.93.80
	Survey to Evaluate PBS			Х	
Stress/QOL	Perceived stress scale (caregiver stress)	Х	Х	Х	α= 0.83 ⁶⁷
	Folkman 1 question regarding what is most stressful.	X			

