Daily Inventory of Stressful Events was taken from the Science of Behavioral Change Research Network list of instruments recommended to assess stress reactivity/stress resilience. The instrument is a semi-structured survey in which participants report whether any stressful events had occurred within the past 24 hours. This instrument yields several variables for each reported stressor including: (a) content classification of the stressor for example, work overload, argument over housework, or traffic problem); (b) subjective severity of stressors; (c) primary appraisals (areas of life that were at risk because of the stressor); and (d) perceived control of the situation." Scores range from 0 to 27. This instrument will be distributed via an automated texted link from Mosio. Pittsburgh Stress Battery is a test of BP response to stress that is indicated as a measure of stress reactivity by the Science of Behavior Change Research Network. The participants are given a series of tests that include the Stroop test, mirror tracing, and mental math. For example, participants will be given three

IRB Approval date:

Version: 08/08/2023

10/05/2022

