trials of basic arithmetic problems lasting one minute per trial. Participants who scores 60% or greater, will advance to the Random-Medium level; those who do not will repeat Easy. Prior to the 3rd trial, the data collector will place the BP cuff on the participants left arm unless contraindicated. At the 30-second mark of the 3rd math trial, the data collector will use an automatic BP machine (clinician grade) to measure systolic BP, diastolic BP and heart rate. Significant Other Collaborator, [name] is a neuropsychologist and will assist with training data collectors to administer the test and interpretation of data. Survey to Evaluate the Pittburgh Stress Battery is a one-question Likert scale to evaluate how challenging the participants found the PBS to be. Selfcare behaviors are measured using Stress Management Practices survey part A, a list of 13 statements such as "I am able to use muscle relaxation techniques to reduce any tension I experience" that is measured on a Likert scale. Scores range from 0 to 52 with higher scores indicating greater use of stress management strategies. Block Food Frequency Questionnaire (includes physical activity) is a validated measure with a food and beverage list that includes 127 items, plus supplementary questions to allow for the adjustment of fat, protein, carbohydrate, sugar, and whole grain content. The questionnaire ascertains the frequency with which each food or beverage was usually consumed, and offers nine continuous responses ranging from "never" to every day" for most foods. The DASH Index that is calculated using data from the Block Food Frequency Questionnaire uses a quintile system to score foods related to the DASH diet. All of the components are equally weighted. Intake of vegetables, fruits (including fruit juice), nuts and legumes, whole grains were scored from 1 (lowest quintile) to 5 (highest quintile). The overall DASH component scores range from 8 to 40. The 4-Item Krousel-Wood Medication Adherence Scale captures four domains of adherence behavior. 78 Scores range from 0 to 4 with a score of 1 or greater indicating lower adherence. These data will be collected at baseline, 3 and 9 months. To reduce participant burden, the Block Food Frequency Questionnaire data will be collected at baseline and 9 months.

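### The only BP procedure described for the Pittsburgh Stress Battery is one reading during the stressor; no resting reading and no reactivity score is described

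*Combined protocol and SAP*

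**What the plan says.** BACKGROUND AND RATIONALE describes stress reactivity as the body's physiological answer to stress, namely "activation of the cardiovascular system by increasing heart rate and BP". That is a change, not a level. MEASUREMENT/INSTRUMENTATION then says: "Pittsburgh Stress Battery is a test of BP response to stress that is indicated as a measure of stress reactivity". With the Daily Inventory of Stressful Events, the battery supplies the mediator for Aim 3.

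The battery has three tasks: Stroop, mirror tracing and mental arithmetic. Only the arithmetic task is described in detail, and it is offered as an illustration: "For example, participants will be given three" "trials of basic arithmetic problems lasting one minute per trial". Two sentences cover BP. The first is: "Prior to the 3rd trial, the data collector will place the BP cuff on the participants left arm unless contraindicated". The second begins "At the 30-second mark of the 3rd math trial, the data collector will use an automatic BP machine (clinician grade) to measure systolic BP" and goes on to DBP and heart rate.

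Table 1 schedules the battery at all three visits and gives reliability coefficients, but no scoring. The Aim 3 paragraph under DATA ANALYSIS names stress reactivity/stress resilience as the mediator and does not say how the variable is derived. Table 1 also lists "Medication list and BP log" at all three visits, under self-care behaviors and with no procedure. On the diet component, the Background refers to: "Solid empirical evidence demonstrating the effectiveness of the DASH diet in reducing blood pressure".

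**The concern.** A reading taken during a stressor is resting BP plus the response to the stressor. Without the resting part, the two cannot be separated, and the plan's definition concerns only the response.

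Stable differences between people in resting BP are not the problem. Randomisation balances them in expectation, and within-person change removes them. The problem is a change in resting BP that differs between arms, which one arm is designed to produce. If MIM DASH lowers resting BP and leaves reactivity alone, the on-task reading still falls and the mediation analysis would report this as lower reactivity.

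The DASH index is also one of the Aim 3 self-care measures. Eating closer to DASH could therefore move the supposed mediator through resting BP, which reverses the path that the analysis is meant to examine. The pilot is intended to identify mechanisms and inform a larger trial, so this misreading could carry forward. A resting value not taken alongside the battery cannot be reconstructed later.

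**Working it through.** The plan gives no figure for this measure, so there is none to reproduce. The check sets the passages side by side and then uses simple algebra.

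**1. Definition against procedure.**
- Definition (Background): an increase in heart rate and BP. This needs a reference value.
- Procedure (MEASUREMENT/INSTRUMENTATION): one time point, within the third arithmetic trial.
- Stroop and mirror tracing: no BP procedure is described.
- Resting, pre-task or recovery reading: none is described.
- Score: none in the measurement section, Table 1 or the Aim 3 analysis.

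**2. Timing of the reading.** Trials last one minute. Two completed trials give 2 × 60 = 120 s of arithmetic, and the reading comes at 120 + 30 = 150 s, not counting pauses. The text says only that the cuff goes on before the third trial. This suggests that no reading precedes the arithmetic task but does not state it.

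**3. What the reading captures.** Let R be resting BP, D the rise under stress, and S = R + D the on-task reading. Let d be the between-arm difference in the change of R from baseline, and r the between-arm difference in the change of D.
- On-task reading: arm difference in change = d + r.
- Task minus rest: (d + r) − d = r.
- With reactivity unaffected (r = 0), the on-task reading shows d and task minus rest shows 0.

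The false signal in the physiological mediator therefore equals d, mmHg for mmHg.

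**4. Can d be taken from the documents?** No. Figure 1 under PRELIMINARY WORK gives a systolic change of −7.2 mmHg for MIM DASH in the preliminary trial. The attention-only value is incomplete as printed, showing −7 and a decimal point with nothing after it. No between-arm difference can be formed from that.

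**5. Price of a difference score.** Assume independent errors with the same SD, e, on each reading.
- Task minus one resting reading: √(e² + e²) = √2 · e = 1.41e.
- Task minus the mean of two resting readings: √(e² + e²/2) = √1.5 · e = 1.22e.

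**6. Workload.** 28 participants × 3 visits = 84 resting measurements if everyone attends. Assuming 6 to 8 minutes for rest and reading, each takes 6/120 = 5.0% to 8/120 = 6.7% of the 120-minute limit per session.

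**The case against.** The strongest reply is that the battery is a named instrument and the protocol need not reproduce its administration. The arithmetic task is explicitly an example, and a neuropsychologist will train the data collectors and help interpret the data. Table 1 quotes separate alpha coefficients for heart rate, SBP and DBP, and alpha is normally computed over several readings, so the instrument may involve more than one. This stands as a limit on the claim. A reader might infer that no resting reading will be taken. The documents do not support that; they show only that none is described. The reply does not supply the reactivity score, which a combined protocol and SAP should define in any case.

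A second reply is that the BP log could serve as rest, since it is scheduled at every visit in both arms. Study home monitors cannot be its only source, because MIM DASH participants receive them with the intervention and controls at study end. The log may therefore hold usable non-task values. But its content is undefined, it is not tied to the battery, and visits may be split into one-hour parts, so a logged value need not come from the same sitting. It cannot be relied on as the reference.

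A reader might also take the −7.2 mmHg as the likely bias. It is a change within one arm, and the comparator's printed leading digit gives no support for a between-arm gap of that size. Equally, the incomplete value does not show that the gap is small.

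Finally, this is a 28-person pilot in which Aim 3 explores potential mediation. That limits the consequences but does not make an on-task level a measure of a rise.

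**Conclusion.** The point holds as a gap between the construct and the procedure described. Followed as written, the battery yields BP during stress, not the rise that the plan calls reactivity. Any between-arm difference in resting BP change would enter the physiological mediator in full. This rests on the additive identity S = R + D and on the plan's own expectation that DASH lowers BP. The size is unknown and cannot be derived from the documents.

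The scope is narrow. Only the physiological measure of the Aim 3 mediator is affected. A reader might infer that Aim 3 as a whole, or the pilot, is compromised. That goes too far: the Daily Inventory is a separate measure of the same mediator, and the Aim 1 feasibility and acceptability criteria do not use BP. This is a cheap improvement worth making, held with medium confidence because a fuller procedure may exist outside these documents.

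**What to change.** **Measurement.** At each of the three visits, take a seated resting SBP, DBP and heart rate with the same device, before the battery begins and in the same sitting. Average two readings if time allows. State which tasks carry BP readings and when, and what the BP log contains.

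**Analysis.** Derive reactivity from task and rest, either as task minus rest or by the instrument's own rest-referenced scoring. Name the score in the Aim 3 section before analysis. Report the task value adjusted for same-visit rest alongside it. Both use the same post-randomisation resting reading, so that feature gives no reason to rank one above the other.

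**If a resting reading is already taken,** write its timing and the score into the protocol; nothing else changes. **If none is taken,** label the variable *BP during stress* and drop the reactivity interpretation.

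**Cost.** A few minutes per visit with equipment already in use. The documents do not say how long the current measures take, so the team must check that the addition fits the session limit. A difference score using a single resting reading has about 1.41 times the error SD of one reading, or 1.22 times with two averaged resting readings, if errors are independent.
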